## 5.6 Study Evaluations

The date of study enrollment will be the date that patient consent is obtained. Patients will be followed through patient's death, date of study withdrawal or 3-months after study enrollment, whichever is earliest.

Patients and close persons will each complete the following surveys and interviews at enrollment (T1), 2-week follow-up (T2) and 3-month follow-up (T3). All study procedures will be conducted by phone, and to maintain privacy, patients and close persons will complete procedures separately. After enrollment (T1), patients and close persons assigned to the intervention will be mailed *A Guide to Conservative Care* and will be given 2 weeks to review the *Guide*. The wording of surveys and interview guides will differ slightly to accommodate subjects who are patients and those who are close persons (see Study Materials). Patients who do not have a close person can still participate in the study and complete the following procedures.

Demographic questionnaire: At T1, patients and close persons will be asked 11 questions about their demographic background, including sex, age, race, prior education, total annual household income, current employment status, self-rated overall health, whether they had previously heard of dialysis or conservative care and sources of this information, relationship to patient (if close person), and whether they are the patient's surrogate decision-maker (if close person). This will take 3 to 5 minutes to complete.

Healthcare goals: At T1, T2 and T3, we will ask patients about their preference for either extending life or preserving comfort. Patients will also have the option of indicating that they are uncertain about which they prefer. Close persons will be asked a similar question about what they perceive the patients' healthcare goals are. This will take 1 to 3 minutes to complete.

Guide questionnaire: At T2, patients and close persons assigned to the intervention will be asked to complete a 4-item questionnaire on their experience with reviewing the *Guide*. This will take 10 to 15 minutes to complete.

Decisional conflict: At T1, T2 and T3, patients will be asked to complete the 16-item Decisional Conflict Scale to assess their preference for dialysis vs. conservative care. Close persons will be asked a similar question about what they would prefer for the patients. This will take about 5 to 8 minutes to complete.

Post-intervention interview: At T2, patients and close persons assigned to the intervention will be invited to answer 4 open-ended questions on the usability of the decision aid. Interviews will be

audio-recorded then transcribed. We estimate that an interview will take 20 to 30 minutes to complete.

Late-intervention interview: At T3, patients and close persons assigned to the intervention will undergo a semi-structured interview to inquire how the decision aid prompted discussion of conservative care with others and their healthcare providers and the outcomes of those interactions. Interviews will take 20 to 30 minutes to complete and will be audio-recorded then transcribed.

Treatment status: At T3, we will ascertain whether patients had died, started dialysis and enrolled in hospice.

## 5.7 Data Analysis

Feasibility and acceptability: As our primary aim, we will estimate the association of the intervention by the difference in patient-reported discussion of conservative care with their healthcare providers at T3. Based on prior work, the rate of patient-reported discussion of conservative care with their health care providers in usual care settings is approximately 29%. The target sample size (n=92) is estimated to provide 80% power (two tailed,  $\alpha=0.05$ ) to detect an absolute difference of 30% or more in rates of patient-provider discussion of conservative care between the intervention and control groups.

As part of our analysis of feasibility and acceptability, we will also calculate point estimates of completion rates and attrition rates and their 95% confidence intervals at T2 and T3. We will further assess user experience of the decision aid by performing a content analysis (an unstructured method of inquiry that facilitates discovery of previously unidentified factors pertaining to a phenomenon) of post-intervention interviews, coding for themes elucidating pros, cons and other considerations with using the decision aid to facilitate decision-making regarding conservative care with their healthcare providers.

Exploratory outcomes: We will assess change in knowledge on conservative care and confidence in making treatment decisions about conservative care (i.e., T3-T1 and T2-T1) based on scores on the Decisional Conflict Scale. To assess for goal concordant treatment decisions, we will measure the distribution of patients who rank life extension or comfort as their highest priority according to those who indicate on the Decisional Conflict Scale at T1, T2 and T3 that they opt for conservative care vs. dialysis. We will perform a content analysis of late-intervention interviews to ascertain detailed information about whether the decision aid prompted discussions on conservative care between patients, their close persons and providers, and code for themes reflecting actions taken by others and providers to subjects' interests and concerns regarding conservative care.

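### The primary between-arm outcome, patient-reported provider discussion at T3, has no listed data source in usual care and no structured item in either arm

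*Protocol*

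**What the plan says.** Section 5.7 (Data Analysis, Feasibility and acceptability) gives the primary aim: "we will estimate the association of the intervention by the difference in patient-reported discussion of conservative care with their healthcare providers at T3". The power statement that follows takes a usual-care rate of about 29% and a 30-point absolute difference "in rates of patient-provider discussion of conservative care between the intervention and control groups". The outcome is therefore a yes/no report from each patient, needed at three months in both arms.

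Section 5.6 (Study Evaluations) sets out the data collection. Its list is introduced with "Patients and close persons will each complete the following surveys and interviews at enrollment (T1", and the sentence runs on to the 2-week (T2) and 3-month (T3) calls. The T3 entries are:

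- Healthcare goals: "we will ask patients about their preference for either extending life or preserving comfort".
- Decisional conflict: "patients will be asked to complete the 16-item Decisional Conflict Scale to assess their preference for dialysis vs. conservative care".
- Late-intervention interview: "At T3, patients and close persons assigned to the intervention will undergo a semi-structured interview to inquire how the decision aid prompted discussion".
- Treatment status: "At T3, we will ascertain whether patients had died, started dialysis and enrolled in hospice".

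Under exploratory outcomes, Section 5.7 says how that interview is used: "We will perform a content analysis of late-intervention interviews to ascertain detailed information about whether the decision aid prompted discussions on conservative care".

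**The concern.** The outcome that defines the primary comparison and sets the sample size does not appear among the procedures meant to collect it. The one T3 procedure on the subject is closed to usual-care patients, and its question could not be put to them: a patient who never received the Guide cannot say how it prompted a discussion.

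Two things could go wrong. If staff follow Section 5.6 as written, no usual-care rate exists at T3 and the randomised difference cannot be estimated. If the intervention-arm rate is instead coded from a 20 to 30 minute interview about such discussions, while controls are asked briefly or in some other way, a difference between arms could reflect how patients were asked and not the Guide.

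**Working it through.** **1. The plan's own figure.** Inputs from Section 5.7: p1 = 0.29, p2 = 0.29 + 0.30 = 0.59, two-sided α = 0.05, power 80%, N = 92. The Abstract (Methodology) gives 1:1 allocation, so 46 per arm. The mean rate is 0.44.

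- Sample size, pooled-variance formula: n = [1.96·√(2·0.44·0.56) + 0.8416·√(0.29·0.71 + 0.59·0.41)]² / 0.30² = (1.376 + 0.563)² / 0.09 = 41.8, so 42 per arm or 84 in total.
- Power at 46 per arm: Φ[(0.30 − 1.96·√(0.4928/46)) / √(0.4478/46)] = Φ[(0.300 − 0.203)/0.0987] = Φ(0.984) = 83.8%.
- Power at 42 per arm: Φ[(0.300 − 0.212)/0.1033] = Φ(0.849) = 80.2%.

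The stated inputs do not give exactly 92, but 92 does deliver at least 80% power on the uncorrected test. The power statement is not in dispute. It matters here because it presupposes a yes/no answer from about 46 patients in each arm.

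**2. Where that answer could come from.** All procedures in Section 5.6:

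| Procedure | Time | Arm | Described as recording provider discussion? |
|---|---|---|---|
| Demographic questionnaire | T1 | both | No; asks whether the person had heard of conservative care, and from what source |
| Healthcare goals | T1, T2, T3 | both | No |
| Guide questionnaire | T2 | intervention | No; experience of reviewing the Guide |
| Decisional Conflict Scale | T1, T2, T3 | both | No |
| Post-intervention interview | T2 | intervention | No; usability of the decision aid |
| Late-intervention interview | T3 | intervention | Touches on it, as an open interview |
| Treatment status | T3 | both | No; death, dialysis, hospice |

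Where no arm is named (demographics, goals, Decisional Conflict Scale, treatment status) I read the entry as applying to both.

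Count: 7 procedures; 4 at T3; 3 of those in both arms, of which 0 are described as recording the outcome; 1 at T3 in the intervention arm only. Structured T3 items listed for the primary outcome: 0 in each arm.

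**3. Other places that might supply it.** Section 5.1 offers interview payments only to those randomised to the Guide, which agrees with controls having no interview. The T1 question on having heard of conservative care is a different question at a different time. Section 5.7 ties its exploratory outcomes to the Decisional Conflict Scale, the ranking of life extension or comfort, and the late-intervention interview, but ties the primary outcome to no instrument.

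**4. What unequal measurement could do (illustration on assumed inputs).** Suppose the true rate is 29% in both arms, and interview probing raises reporting in the intervention arm alone by 5, 10, 15 or 20 points. The protocol gives no figure for this. The power formula from step 1, with 46 per arm, gives the chance of a significant result. For 10 points (29% against 39%, mean 34%): Φ[(0.10 − 1.96·√(0.4488/46)) / √(0.4438/46)] = Φ[(0.100 − 0.194)/0.0982] = Φ(−0.953) = 17%. For 5, 15 and 20 points the results are 7%, 32% and 50%. The nominal two-sided level is 5%.

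**The case against.** The strongest reply is that this is an omission and not a contradiction. No sentence in Section 5.6 says usual-care patients are not asked, and Section 5.7, by requiring the outcome in both arms, suggests that they are meant to be. The survey wording sits in Study Materials that are not shown, and a suitable question may be there. If it is, the defect shrinks to a missing cross-reference and the consequences above fall away. The descriptions in 5.6 are also not full inventories: 5.6 presents the Decisional Conflict Scale as assessing treatment preference, while 5.7 draws knowledge and confidence from it.

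Much of this is fair. The two sections are out of step; they are not flatly opposed. The harm is conditional on the procedures being run as listed, and the illustration in step 4 shows only what assumed reporting gains would do. Asking the question ahead of the interview is sound practice, not something the protocol's text demands.

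Three things still stand. Section 5.6 refers to Study Materials in a sentence about wording differences between patients and close persons, not as a source of further procedures. Nothing in 5.6 suggests that any shared instrument covers provider discussion. And no place in the protocol gives a T3 source for the control rate. Nor can this be left to a statistical analysis plan, which cannot supply an answer that was never collected.

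**Conclusion.** The concern holds. Section 5.7 powers a between-arm difference at T3 for which Section 5.6 lists no structured question in either arm and no source of any kind in usual care. If the procedures are run exactly as listed, the control rate is unobserved and the primary comparison cannot be made, whatever the sample size. If the gap is filled differently by arm, the comparison is open to measurement bias.

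This rests on reading Section 5.6 as the working list of procedures, and on procedures without a named arm applying to both. Confidence is medium because the Study Materials could already hold the item. It should be corrected; the sample size and power statement need no change on this account.

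**What to change.** In Section 5.6, list one T3 question on whether the patient has discussed conservative care with a healthcare provider. Put it in the same words to patients in both arms, and ask it before and apart from the late-intervention interview. In Section 5.7, name that item as the source of the primary outcome. If the Study Materials already contain such a question for both arms, listing it in 5.6 and citing it in 5.7 is enough.

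The cost is one short question at a three-month call that usual-care patients already receive, one line in 5.6 and one phrase in 5.7. If the question has not been asked so far, patients already past T3 could be recovered only by a further contact, so the change is best made early.

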### **Methodology**

We will recruit 92 patients aged 75 years and older with advanced CKD as defined as an estimated glomerular filtration rate  $<25$  ml/min/1.73m^2 from UW Medicine and VAPS. We will ask patients to invite up to 1 close person as defined as a relative or friend who assists them with their medical care to also participate in the study. We will randomize patients and their close persons in a 1:1 fashion to either usual care or receipt of the decision aid. Participants will complete all study procedures by phone and over a total of three phone study visits.

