## **5.0 Study Procedures**

### **5.1 Study Design**

We will conduct a randomized pilot study to test the feasibility and acceptability of a decision aid, *A Guide to Conservative Care*, among older patients with advanced kidney disease and their family members using interview methodology and questionnaires. We will also explore preliminary outcomes including decisional uncertainty and goal concordant care to inform a future clinical trial. We aim to enroll 92 patients with kidney disease and up to 92 of their close persons in this study. All study procedures will be completed over the phone. It will take a total of 3 phone calls to complete all study procedures. Each phone call will take a total of 30 to 45 minutes.

For completing the study procedures, we will give participants a \$20 gift card at the start of the study, a \$10 gift card at 2-week follow up, and a \$10 gift card at 3-month follow up. For those who are chosen at random to receive the *Guide*, we will give an additional \$20 gift card for each interview that you complete: 2-week follow up and a 3-month follow up.

The principal risk posed to study subjects is the potential loss of confidentiality. The proposed work requires the collection of protected health information to identify and recruit eligible subjects and contact and maintain follow up with participating subjects. We will also audio-record interviews with subjects during which personal information might be spoken.

To minimize this risk, we have outlined steps below to safeguard patient confidentiality. These include restricting data analyses to only de-identified data files, keeping separate a crosswalk file linking study ID with personal identifiers and data analysis files, storage of data on password-protected secure servers and key-locked filing cabinets accessible to only study team members who have completed training in the protection of human subjects, and the aggregation of study data for presentations and publications in order to conceal the subjects' identities.

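### Does the 80% power stated for 92 patients fail to follow from the protocol's own inputs?

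*Protocol*

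**What the plan says.** Section 5.7 makes patient-reported discussion of conservative care with providers at T3 (three months) the primary comparison. It takes from prior work that the rate "in usual care settings is approximately 29" per cent. It then says "The target sample size (n=92) is estimated to provide 80% power" (two-sided, alpha 0.05) "to detect an absolute difference of 30% or more in rates of patient-provider discussion of conservative care".

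The same 92 appears elsewhere as a recruitment figure. The Methodology part of the Abstract says "We will recruit 92 patients aged 75 years and older" and specifies 1:1 randomization. Section 5.1 says "We aim to enroll 92 patients with kidney disease".

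On follow-up, section 5.6 says: "Patients will be followed through patient's death, date of study withdrawal or 3-months after study enrollment, whichever is earliest". Section 5.7 plans to estimate completion and attrition rates with confidence intervals. No test, evaluable number or expected loss accompanies the power statement.

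**The concern.** Every input to the calculation is printed, so the output should be reproducible, and the standard formulas do not give 80% at 92. Uncorrected methods give more and corrected or exact methods give less.

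The denominator also looks wrong. The power is attached to everyone enrolled, but the outcome is a self-report three months later in people aged 75 or older with advanced kidney disease. Some may die, withdraw or not be reached, and the protocol itself expects to measure attrition. If 92 was meant as the evaluable number, power after losses would fall below the figure a reader takes away. This is the only planning figure for the primary comparison.

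**Working it through.** **Inputs.** From section 5.7: control rate p1 = 0.29; difference 0.30, so p2 = 0.59; two-sided alpha 0.05 (z = 1.960); power 80% (z = 0.842). From the Abstract, 1:1 allocation, so 92 patients means n = 46 per arm.

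**Pooled normal approximation.** The mean rate is 0.44.
- Null term: √(2 × 0.44 × 0.56) = √0.4928 = 0.7020.
- Alternative term: √(0.29 × 0.71 + 0.59 × 0.41) = √0.4478 = 0.6692.
- Required n per arm: (1.960 × 0.7020 + 0.842 × 0.6692)² / 0.30² = 1.939² / 0.09 = 41.8, so 42 per arm and 84 in total.
- Power at n = 46: Φ[(0.30 × √46 − 1.960 × 0.7020) / 0.6692] = Φ(0.984) = 83.8%.
- Power at n = 42: Φ(0.849) = 80.2%.

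**Other methods at 46 per arm, all 92 evaluable**

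| Method | Power |
|---|---|
| Unpooled normal approximation | 86.0% |
| Arcsine | 83.8% |
| Uncorrected chi-square, exact enumeration | 83.1% |
| Continuity-corrected formula | 77.8% |
| Fisher's exact, enumeration | 77.2% |

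The stated 80% is not reproduced by any single method. It falls between the uncorrected and the corrected or exact results. Rounding of the control rate does not explain the gap: over control rates from 25% to 40% with a 30-point difference, pooled power at 46 per arm stays at or above 83.2%.

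**The gap on the scale of the effect.** With 92 evaluable and 80% power, the detectable difference is 28.6 points by the uncorrected approximation and about 31 points by Fisher's exact test (80.05% at 31 points). The protocol says 30.

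**Losses before T3.** The protocol gives no rate, so these are assumptions. Pooled approximation, patients with data only:

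| With T3 data | Lost of 92 | Power |
|---|---|---|
| 92 | 0 | 83.8% |
| 84 | 8 (8.7%) | 80.2% |
| 83 | 9 (9.8%) | 79.7% |
| 78 | 14 (15.2%) | 77.1% |
| 74 | 18 (19.6%) | 74.9% |

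An allowance of 8% on 84 gives 84 / 0.92 = 91.3, rounded up to 92.

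**Is eight losses a real limit?** No. Exact power moves in a saw-tooth as n changes. For the uncorrected chi-square test, enumeration gives 82.8% at 42 per arm, 81.3% at 41 per arm (10 lost) and 79.7% at 40 per arm (12 lost). The crossing between 8 and 9 losses belongs to the normal approximation only.

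**The case for a change.** The strongest case for a change is that the sentence is inaccurate under every reading. If 92 is 84 plus an allowance, then 80% belongs to 84 patients with T3 data and not to the 92 named. If all 92 are evaluable, an uncorrected test gives about 84%. If Fisher's exact test is used, 92 falls short with no loss at all, and power is 66.2% with 74 evaluable. If patients without a report were counted as having had no discussion, power by the pooled approximation would be 76.3% at 10% loss and 67.9% at 20%. The correction would take a sentence or two.

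Part of this stands. The basis of the 92 is undocumented, and the wording does not separate enrolled from evaluable patients. The rest depends on things the protocol does not fix. The choice between a corrected and an uncorrected test, and the handling of missing T3 reports, are commonly settled in the analysis plan, which is not at hand. The loss rates are hypothetical: follow-up lasts three months, is done by phone, and carries gift cards at both follow-up contacts (section 5.1). Estimating attrition is a normal aim of a pilot and does not imply that it will be heavy.

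**Conclusion.** No change is needed. With all 92 evaluable, the stated 80% is 3.8 points below the pooled result and 2.8 points above the Fisher result. In terms of the detectable difference, the discrepancy is 1.4 points one way and about 1 point the other. That is within what a figure described as an estimate, built on an approximate control rate, can carry. The most natural explanation is 84 evaluable patients plus an allowance of about 8 to 9%. On that reading the number enrolled is adequate and only its derivation is missing.

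This conclusion assumes a control rate near 29%, equal arms, and either an uncorrected test with modest losses or an exact test with almost none. Losses near 20% would bring uncorrected power to about 75%, but nothing in the protocol supports that rate. Stating the test, the evaluable number and the allowance would be tidier. It would keep 92 patients, change no procedure, and leave the estimated difference at T3 as it is. For a pilot meant to inform a later trial, that gain does not justify an amendment.

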## 5.8 Withdrawal of Subjects

Subjects will be informed during the consent process and at each study phone visit that they can choose to withdraw from the study at any point in time.

There are no anticipated circumstances under which subjects will be withdrawn from the research without their consent. There are no anticipated consequences of a subject's decision to

withdraw from the research. During data collection, study interviewers will assure participants that they can, at any time during the interview, refuse to answer any questions asked of them and may at any time elect to withdraw from the study. If a participant elects to withdraw during the phone call, the interviewer will immediately end the interview or questionnaires.

## **6.0 Reporting**

We do not anticipate any adverse events that might occur. However, any and all unanticipated problems, serious adverse events and protocol deviations will be recorded and reported immediately to the study Principal Investigator. Any serious adverse events and/or serious problems will be reported to the IRB within 5 business days. Additionally, the ISO and Privacy Officer will be notified within one hour of any improper use or disclosure of study data. The Principal Investigator will be the monitoring entity responsible for ensuring that all measures related to data security and protection of subject privacy and confidentiality are being followed.

Subjects will be informed to contact the PI for all urgent and non-urgent questions and concerns at the following: [name], [contact].

